STUDY PROTOCOL

The Protocol of the Application of Economics & Social Psychology to Improve Opioid Prescribing Safety Trial 2
(AESOPS-2): Availability of Opioid Harm

Principal Investigator:

[name]., Associate Professor, University of Southern California
[name], Professor, University of Washington

Supported by:

The National Institute on Aging
R33AG057395

Version date: September 18, 2025

A. Background and Status of the Problem

The objective of this study is to evaluate an extension to an existing quality improvement program in Los Angeles County addressing opioid stewardship. Much of the increase in opioid prescribing rates from 1999 until the past decade was driven by the liberal attitudes toward prescribing opioids for non-cancer pain [1, 2]. Opioids carry significant risks of overdose and addiction, and there is evidence that non-opioid alternatives are safer and as effective [3]. The greater availability of prescription opioids has been accompanied by an alarming rise in the negative consequences related to opioid use. In 2017, there were 17,029 prescription opioid overdose deaths in the US [4]. The costs of prescription opioid adverse outcomes are staggering. Aggregate costs for prescription opioid harms are estimated at over \$78.5 billion (in 2013 USD), and almost 25% of the aggregate economic burden is publicly funded (for instance, through Medicaid, Medicare, and veterans' programs) [5].

In 2016, the United States Centers for Disease Control and Prevention (CDC) issued the "CDC Guideline for Prescribing Opioids for Chronic Pain" which encourages the use of alternatives to opioids and other practices that minimize harm to patients [6]. Despite the introduction of this guideline, primary care clinicians, who prescribe 45% of all opioid prescriptions in the US, report practical challenges in implementing these recommendations [7]. The dynamics of opioid use make following guidelines difficult. Since opioid analgesia from a given dose declines with chronic use due to tolerance, doses end up increasing the chance of harm. Over time, the primary benefit of opioids for many patients is the avoidance of withdrawal. As patients become dependent on opioids, they may misconstrue the easing of withdrawal hyperalgesia that occurs with the consumption of opioids as ongoing effectiveness, and they may become reluctant to stop opioids [8]. More cautious opioid prescribing (including fewer new starts, avoidance of high doses, and slow, collaborative tapers for those already on high dose long-term therapy) may improve the balance of benefits and harms for patients with chronic pain. To become a more cautious prescriber, a clinician may need to be informed that opioid risks are present and relevant to his or her own patients.

A prior quality assurance study found that clinicians judge risk to patients as greater after information about a patient's fatal overdose is available to them [9]. Of course, not all clinicians prescribe to patients who suffer a fatal overdose, so the question remains whether providing feedback concerning non-fatal overdoses will have a similar impact on prescribing clinicians. Thus, the Application of Economics & Social psychology to improve Opioid Prescribing Safety (AESOPS) Availability of Harm trial will test whether or not providing feedback to clinicians on both fatal and non-fatal overdoses results in more judicious prescribing of opioids. The objective of the AESOPS Availability of Harm trial is to dampen the intensity and frequency of opioid prescribing in accordance with the Centers for Disease Control and Prevention recommendation to "go low and slow". We

aim to accomplish this by increasing the mental availability of risks associated with opioid use by notifying clinicians of harmful patient outcomes.

B. Method of Study in Detail

a) Purpose and hypotheses to be tested:

Study Synopsis

Application of Economics & Social psychology to improve Opioid Prescribing Safety (AESOPS) Trial 2 is a multi-site randomized trial that takes place among a clinic organization in Los Angeles, California (AltaMed Health Services) and one in Chicago, Illinois (Northwestern University). Participants in the trial are clinicians. Observations are visits where opioids are prescribed. Clinicians are randomized to receive either: 1) guidelines on opioid prescribing, or 2) information on an opioid harm experienced by one of their patients (non-fatal or fatal overdose). In Los Angeles, fatal overdose letters are already required by the County, therefore, only non-fatal overdose letters will be sent to clinicians in Los Angeles. These will be signed by the County Public Health Officer. In Chicago, Illinois, both types of letters will be sent. Outcomes are milligram morphine equivalents ordered by each participating clinician per week. A secondary outcome is referrals to medication assisted treatment. These data are collected from the electronic health record systems at AltaMed and Northwestern Medical Center. Determining overdoses involves connecting data on overdoses between hospital systems, or in the case of Illinois, state vital records. More specifically, non-fatal overdoses in Los Angeles connect opioid prescribing at AltaMed with Los Angeles County emergency department data (See Appendix 1, Figure 1a), non-fatal overdoses at Chicago's Northwestern University involve a search of the internal database that connects that University's outpatient clinic data with emergency department data (See Appendix 1, Figure 1b), and fatal overdoses among patients at Northwestern connect data from that institution with Illinois State Vital records (Illinois Department of Public Health (IDPH); See Appendix 1, Figure 1c). A pilot study was originally approved for the data exchange in Figure 1c and the secure data sharing exercise was successful.

The goal of the project is to dampen the intensity and frequency of opioid prescribing and to increase awareness and use of medication assisted therapy for persons with opioid use disorder through a cluster randomized trial. Overdose notification letters (See Appendix 2 and 3) will be sent to primary care clinicians randomized to the experimental study arm and meeting inclusion criteria at AltaMed Health Services or Northwestern Medicine. Both letters will include "if/when/then" language which advises the clinician to keep the letter's recommendations close when their next patient presents with pain. Clinicians notified of their patient's overdose will be compared to a control group receiving guideline education and no notification of their patient's overdose (Appendix 6). To quantify the effect of the notification letter, we will measure the change in clinician weekly milligram morphine equivalent (MME) prescribed to all of their patients in 6-month periods before and after receiving overdose feedback letters. The secondary outcomes include the change in proportion of patients prescribed at least 50 daily MME, buprenorphine referrals for medication assisted therapy, and access rates for referral links included in the letter.

Because the letters include patient identifying information linked to outpatient prescribing records, we requested a HIPAA waiver of authorization to match outpatient records to mortality and non-fatal overdose records. The research could not feasibly be conducted if research participants' authorization were required. AltaMed will release information under the auspices of a waiver of HIPAA authorization. USC and AltaMed have a fully executed Business Associates Agreement, Memorandum of Understanding and Data Use Agreement; Northwestern and IDPH and USC and Northwestern have a fully executed Data Use Agreement. AltaMed and Northwestern will cede to the County IRB as the IRB of record for this study.

To create the list of overdose patients for whom opioids were prescribed, outpatient records will be linked to the emergency department and, in the case of Northwestern patients, IDPH death records. Overdose data will be linked with outpatient records using matching software that complies with institutional security and privacy standards at IDPH and Los Angeles County. Where an existing direct link code is available (e.g. MRN), we will use the code.

Primary hypotheses:

1. Clinicians randomized to the overdose notification group will exhibit a greater reduction in weekly MME from the pre- to post-period compared to clinicians randomized to the control group for fatal and non-fatal overdoses.
2. Among the clinicians who prescribed at least one opioid in the study period, those randomized to the overdose notification group will exhibit a greater reduction in the proportion of a clinician's patients prescribed at least 50 daily MME from the pre- to post-period compared to clinicians randomized to the control group for fatal and non-fatal overdoses.

b) Number of subjects:

AltaMed Health Services is a private health system in Los Angeles, California. AltaMed has 35 clinics with 134 clinicians with 17,674 such patients. Clinicians meeting inclusion criteria will be enrolled in the study. Northwestern Medicine is a regional health system affiliated with an academic medical center located in the Chicago region of Illinois and includes 60 primary care clinics that contain 387 clinicians with 12,552 patients using chronic opioid therapy for noncancer pain—on opioids for greater than three months.

c) Mechanism for subject selection or exclusion:

Eligible physicians and patients will be identified using outpatient opioid prescribing data

from electronic medical records. A clinician is eligible for inclusion if: 1) s/he prescribed a qualifying scheduled drug to a patient in the 12 months prior to their fatal or non-fatal overdose 2) the patient is 18 years old or older at the time of the overdose, 3) s/he practices within a health system enrolled in the study, and 4) the overdose occurs during the 12-month observation period.

A patient is eligible for identification in a physician notification if s/he (a) has been prescribed an opioid by an eligible clinician (b) has a documented overdose event in EHR or mortality data. Patients without overdose events will be excluded. Patients with fatal overdoses in Los Angeles County will be excluded to avoid redundancy with existing notification practices.

[figure not shown]
d) Duration of intervention:

The duration of the overdose notification intervention is one day.

e) Total duration which study will be performed (data collection, intervention, and analysis period):

Non-Fatal Overdose Records: Northwestern University. A one time data extract will be generated at the beginning of the study, looking back 24 months to identify clinicians who prescribed a qualifying scheduled drug to a patient in the 12 months prior to their non-fatal overdose. The list of patients with outpatient opioid prescriptions will be used to retrieve overdose records that occur within the 12 month observation period. Emergency department and outpatient records at Northwestern are secured in the same EHR. The list will be delivered to Northwestern study staff to prepare notification letters.

Quarterly Fatal Overdose Records. Opioid-related death data will be gathered from the Illinois Department of Public Health (IDPH). Each quarter, Northwestern study personnel will securely transfer IDPH a list of identifiers for patients who received an opioid prescription at a participating clinic. IDPH will use this information to identify if the patient is deceased. If so, IDPH will send back the date of death, cause of death, and whether the death was opioid-related via a secure file transfer process to Northwestern Medicine. IDPH will not send back information if a patient is not deceased. Analysts at Northwestern Medicine will link opioid-related decedents to identify opioid prescriptions and prescribers. The list of patients with fatal overdose will be returned to Northwestern Medicine for preparation of notification letters.

As described above, each system's enterprise software and identifiers will be employed to match patients and their providers across settings.

Allocation Data Set and Study Identifiers. Each patient and prescriber will be assigned a unique study identifier based on outpatient data before overdose data is added. The

randomization and allocation procedure described in Experimental Procedures (below) will be applied by the Los Angeles Department of Health Services and Northwestern Study Staff to create the final list of notifications.

HIPAA Limited Data Set. At the conclusion of the study period, each health system will prepare a HIPAA limited data set for analysis. The data set will include dates of overdose events, post-intervention opioid prescribing, and unique study identifiers. Study assignment, physician notification information, and overdose data from Los Angeles County Department of Public Health will be de-identified retaining unique study identifiers. Data will be transferred to USC Schaeffer Center HIPAA data enclave for analysis. No USC study personnel will have access to any patient identifying information. Links between identified data and study identifiers will be destroyed at the conclusion of the analysis.

C. List of Experimental Procedures to be Employed

a) List and detail risks:

- Mitigation of risk to participating physicians
 - Letters are a normal aspect of quality review. Letters notifying clinicians of a fatal overdose are mandated in Los Angeles County. [see LA County Board of Supervisors Meeting <https://youtu.be/hBefHyAL5I8>]. Therefore, risks faced by participants do not exceed that of normal clinical practice. We will take every precaution to mitigate risk to participating clinicians by keeping this disclosure private. All correspondence will be private and conducted through delivery using one of the following approaches: 1) US Postal Service, 2) institutional email, or 3) Epic inbox message, and will not be shared outside of the study.
- Mitigation of risk to patients
 - Risk of correspondence adds no additional risk compared to what is already being sent in the mail or by email (such as prior authorization letters by insurers or billing). Further, the HIPAA conduit exception allows HIPAA-covered entities to use the US Postal Service, institutional email, and Epic inbox messaging for the transmission of personal health information. US Letters and email are private and tampering with private mail is a federal offense.
 - The NIH has established a Data and Safety Monitoring Board for this study. The board consists of individuals with expertise in opioids, overprescribing, biostatistics or research methods. When notified of an unanticipated event following the intervention, the board will convene and make a decision as to whether the study should continue.
 - A potential risk is an adverse event, defined by the CDC as an abrupt

discontinuation of opioids for persons whose most recent prescription exceeds 49 MME daily dose; or as reported to study staff (10).

If there is a significant difference in the prevalence of these adverse events or overdoses between the treatment and control groups, the differences will be reported to the Data and Safety Monitoring Board and in the publication of the study results. *It is important to note that prior quality evaluations of these letters observed no additional risk of abrupt changes to opioid prescribing upon receipt of a letter (<https://pubmed.ncbi.nlm.nih.gov/30093595/>).*

- Management of overdose and prescribing data poses no more than minimal privacy risks. USC, health systems and IDPH comply with all local and federal security regulations protecting privacy. Identified patient data will be destroyed after the notifications have been prepared. A HIPAA Limited Data Set that includes outpatient prescribing records, overdose events, and notification status will be transferred to USC for data analysis in USC's HIPAA compliant enclave.

b) Experimental Procedures:

Randomization and Allocation. Overdose clusters are the units of randomization in this study. A cluster consists of all clinicians who prescribed one or more of the included scheduled drugs to the patient in the year prior to the overdose. Overdose clusters will be randomized to the overdose notification group or the control group, stratified by the health system which defines the cluster in the year prior to the overdose event.

Allocation will be concealed until after the study groups are assigned. Clinicians who practice at multiple clinics will be assigned to the clinic at which the majority of their visits occurred in the year prior to the overdose event. If clinicians belong to more than one cluster (have multiple patients with opioid-related overdoses), they will be randomly assigned to one of those patients and placed in the corresponding study group. If clinicians belonging to more than one cluster are randomized to the intervention group, they will only receive an overdose notification regarding the one patient to whom they were randomly assigned.

Intervention. Clinicians in the intervention group receive a letter notifying them of their patient's fatal or non-fatal overdose. As described above, we will identify overdoses from electronic health record data from emergency departments and state vital records.

If randomized to the overdose notification group, physicians who prescribed a qualifying prescription to the deceased or surviving patient in the year prior to their overdose will be informed of the overdose via letter. The letters will alert prescribers to the patient's opioid-related overdose, recommend the use of their state's PDMP, and list evidence-based interventions to lower opioid-related overdoses (Appendix 2 and 3).

Controls. Clinicians in the control group will receive guideline education in the form of the CDC pocket guide and no notification of a patient overdose event (See Appendix 5). https://www.cdc.gov/drugoverdose/pdf/TurnTheTide_PocketGuide-a.pdf

D. Statistical Analysis Plan

Patients who experienced an opioid overdose will be randomized to either the letter intervention or control. We will analyze how the prescribing behavior of those patients' clinicians changed pre-to-post intervention. We will use means and medians for continuous measures for sample descriptive statistics, frequencies for count data and standard deviations, and interquartile ranges for variance. We will evaluate changes in opioid prescribing rates by group using an intent-to-treat difference-in-differences regression model on clinician hydrocodone morphine equivalent weekly dose. The coefficient for the group assignment, overdose type, and time interaction, also known as the difference-in-differences estimator, denotes the change over time in 5 MME hydrocodone pills for prescribers in the intervention group compared to prescribers in the control group for both fatal and nonfatal overdose victims. The use of a mixed-effects hierarchical knotted spline Poisson regression model offers a flexible way to accommodate non-linear trends in prescribing by group before and after introducing the intervention. This model places a knot at the intervention start date allowing slopes before and after the introduction of the intervention to vary for each group. Our primary outcome is the daily average number of 5 MME hydrocodone pills. If we have an excess of data clustering at zero, indicating weeks during which a physician wrote no opioid prescriptions, we will use a zero-inflated or left-censored regression. The regression model estimating the association between letter assignment and weekly 5 MME hydrocodone pills prescribed is shown in Eq. 1:

$$(pills)_{ijk}^* = \beta_1 + \beta_2 Time_{ij} + \beta_3 (Time_{ij} - t^*) + \beta_4 Group_i + \beta_5 Overdose Type_k + \beta_6 Group_i * Overdose Type_k + \beta_7 Time_{ij} * Group_i + \beta_8 (Time_{ij} - t^*) * Group_i + \beta_9 Time_{ij} * Overdose Type_k + \beta_{10} (Time_{ij} - t^*) * Overdose Type_k + \beta_{11} Time_{ij} * Group_i * Overdose Type_k + \beta_{12} (Time_{ij} - t^*) * Group_i * Overdose Type_k + \eta + \delta_{i(k)} + error$$

where $(pills)_{ijk}^*$ denotes the dependent variable for clinician i in week j , $Time_{ij}$ is the study week indexed by j , t^* is the spline knot for the start of the intervention, $(Time_{ij} - t^*)$ is a truncated line function that is equal to $(Time_{ij} - t^*)$ when $Time_{ij} > t^*$ and 0 otherwise to allow for nonlinear trends in prescribing following the intervention, $Group_i$ is dichotomous for the overdose notification intervention group, $Overdose Type_k$ is dichotomous for a fatal overdose, η is the clinic random effect, and $\delta_{i(k)}$ is the random effect for each clinician i who prescribed to patient k who suffered an overdose.

The mixed logistic regression model for our secondary outcomes is shown in Eq. 2:

$$(high dose Rx)_{ijk} = \beta_1 + \beta_2 Time_{ij} + \beta_3 Group_i + \beta_4 Overdose Type_k + \beta_5 Group_i * Overdose Type_k + \beta_6 Time_{ij} * Group_i + \beta_7 Time_{ij} * Overdose Type_k + \beta_8 Time_{ij} * Group_i * Overdose Type_k + \eta + \delta_{i(k)} + error$$

where $(high\ dose\ Rx)_{ijk}$ is whether the visit had a high dose prescription of 50 MME or greater (yes vs. no) for clinician i , $Time_{ij}$ is the study period (pre- vs. post-intervention) indexed by j , $Group_i$ is dichotomous for the overdose notification intervention group, $Overdose\ Type_k$ is dichotomous for a fatal overdose, η is the clinic random effect, and $\delta_{i(k)}$ is the random effect for each clinician i who prescribed to patient k who suffered an overdose. We will compute the estimated pre- to post-intervention change in the mean proportion of high dose patient visits for each of the four intervention groups: nonfatal control, nonfatal letter, fatal control, fatal letter. The proportion will be calculated by dividing the total number of patient visits where an opioid of at least 50 MME was prescribed by the total number of opioid prescriptions.

E. Privacy of Individuals and Confidentiality of Data

We will utilize two types of data for this study:

Quality assurance program data: Data will include patient and physician identifiers. USC, health systems and IDPH comply with all local and federal security regulations protecting privacy. Identified patient data will be destroyed after the notifications have been prepared.

Program evaluation data. A HIPAA Limited Data Set that includes outpatient prescribing records, overdose, and notification status will be transferred to USC for data analysis in USC's HIPAA compliant enclave. Management of overdose and prescribing data poses no more than minimal privacy risks.

Waiver of Informed Consent. As our study design necessitates that physicians not be made aware they are participants in a research study, we are requesting a waiver of consent. We provide the following justification for this clinician waiver of consent: The Common Rule" (§46.116) specifies that informed consent can be waived when: "(1) The research involves no more than minimal risk to the subjects; (2) The research could not practicably be carried out without the requested waiver or alteration; (3) If the research involves using identifiable private information, the research could not be practicably carried out without the identifiable information; (4) The waiver or alteration will not adversely affect the rights and welfare of the subjects; [and] (5) Whenever appropriate, the subjects will be provided with additional pertinent information after participation."

Debrief. We will have a participant debrief following completion of the study. Clinicians will be sent a debriefing statement (see Appendix 6) which contains the following information: a description of the nature and purpose of the study, specification of what data were collected about participants, and that the data will be aggregate and not linked back to individual providers or patients.

References:

1. [G. P. Guy Jr et al., "Vital Signs: Changes in Opioid Prescribing in the United States, 2006-2015," *MMWR Morb. Mortal. Wkly. Rep.*, vol. 66, no. 26, pp. 697-704, Jul. 2017.](#)
2. [D. Boudreau et al., "Trends in long-term opioid therapy for chronic non- cancer pain," *Pharmacoepidemiol. Drug Saf.*, vol. 18, no. 12, pp. 1166-1175, 2009.](#)
3. [E. E. Krebs et al., "Effect of Opioid vs Nonopioid Medications on Pain- Related](#)

Function in Patients With Chronic Back Pain or Hip or Knee Osteoarthritis Pain: The SPACE Randomized Clinical Trial," JAMA, vol. 319, no. 9, pp. 872–882, Mar. 2018.

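### Abrupt stops above 49 daily MME, the plan's own named adverse event, can be credited as benefit, and section D has no analysis that would show it

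*Combined protocol and SAP*

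**What the plan says.** Section C.a (List and detail risks) names the harm. The sentence opens "A potential risk is an adverse event, defined by the CDC as an abrupt" and continues "discontinuation of opioids for persons whose most recent prescription exceeds 49 MME daily dose"; events reported to study staff also count. If the prevalence of these events or of overdoses differs significantly between arms, the difference goes to the Data and Safety Monitoring Board and into the publication. No test, significance level, denominator or time window for abruptness is given, and section D does not mention the comparison.

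Section B.a sets out the hypotheses. Under Hypothesis 1, notified clinicians "will exhibit a greater reduction in weekly MME from the pre- to post-period" than controls; the synopsis takes the MME as that "prescribed to all of their patients in 6-month periods before and after receiving overdose feedback letters". Under Hypothesis 2, they "will exhibit a greater reduction in the proportion of a clinician's patients prescribed at least 50 daily MME". Section D (Eq. 2) models the latter at visit level and computes the proportion by "dividing the total number of patient visits where an opioid of at least 50 MME was prescribed by the total number of opioid prescriptions".

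Section A describes the intended change as more cautious prescribing: fewer new starts, avoiding high doses, and "slow, collaborative tapers for those already on high dose long-term therapy".

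**The concern.** The harm and the high-dose outcome use practically the same threshold (above 49 and at least 50 differ only for doses between the two), and both outcomes improve when such a patient disappears from the prescribing record. Neither Eq. 1 nor Eq. 2 distinguishes a patient who was tapered from one who was cut off. If the letters act partly through abrupt stops, those stops enter the efficacy estimate in the favourable direction. A positive result would then be hard to read as more judicious prescribing, which is the claim the trial is meant to test.

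**Working it through.** The documents give no adverse-event rate, sample-size calculation or effect size, so there is no planned figure to reproduce. The check is on direction, then on size under stated assumptions.

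**1. Weekly MME.** Stopping a patient at daily dose D removes 7D MME per week. Reducing the same patient to t (below 50) removes 7(D − t). The stop removes 7t more, which is positive for any t above zero. At assumed doses of 50, 90 and 120 MME, one stop removes 350, 630 and 840 MME per week, or 70, 126 and 168 pills of 5 MME.

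**2. High-dose share.** Take h high-dose patients among n opioid patients, one prescription each.
- Stop one, with the section D denominator: h/n becomes (h − 1)/(n − 1). The fall is (n − h)/[n(n − 1)], positive whenever h < n.
- Reduce one below 50: h/n becomes (h − 1)/n. This is lower than after a stop by (h − 1)/[n(n − 1)].

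So a stop usually lowers the share, but slightly less than a reduction does. Example (assumed): 10 of 40 is 25.0%. Three stops give 7/37 = 18.9%; three reductions give 7/40 = 17.5%.

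**3. Both outcomes in one panel (assumed).** Take 20 patients at 60 MME and 80 at 20 MME: 7 × (1,200 + 1,600) = 19,600 MME per week, high-dose share 20.0%. Change only 4 high-dose patients:

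| Change | Fall in daily MME | Fall in weekly MME | Share after |
|---|---|---|---|
| Stopped | 240 of 2,800 | 8.6% (to 17,920) | 16/96 = 16.7% |
| Reduced to 49 | 44 of 2,800 | 1.6% | 16/100 = 16.0% |
| Reduced to 40 | 80 of 2,800 | 2.9% | 16.0% |
| Reduced to 30 | 120 of 2,800 | 4.3% | 16.0% |

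On weekly MME the stop scores 240/120 = 2.0 to 240/44 = 5.5 times as well as the reduction. The doses only illustrate the arithmetic.

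**4. What reaches the treatment contrast.** Section D estimates a difference-in-differences. Stops that occur equally in both arms largely cancel; only an excess in the letter arm counts as effect.

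**5. Would the section C.a comparison show that excess?** Assume a two-sided 0.05 test, n at-risk patients per arm, and no clustering. With p̄ the mean of p1 and p2, power = Φ{[|p1 − p2| − 1.96√(2p̄(1 − p̄)/n)] / √[(p1(1 − p1) + p2(1 − p2))/n]}.

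| Event rates (assumed) | n = 50 | n = 100 | n = 200 |
|---|---|---|---|
| 5% vs 10% | 16% | 27% | 48% |
| 10% vs 15% | 11% | 19% | 33% |
| 10% vs 20% | 29% | 51% | 80% |

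Randomisation is by overdose cluster, so power at these patient numbers would probably be lower. A real excess could easily miss the reporting trigger.

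**The case against.** The strongest reply is that the plan does not ignore this harm. Section C.a compares it by arm, sends significant differences to the monitoring board and publishes them; the board also convenes when told of an unanticipated event. Efficacy on prescribing volume with harm as a separate safety comparison is a conventional structure, and reducing the intensity and frequency of prescribing is the stated aim. Section C.a reports that earlier evaluations of such letters saw no added risk of abrupt changes, and the letters themselves advise slow tapers with pauses. All of this stands, and it limits the point. It does not close the gap, because the safety result is reported only after an undefined significance test and cannot show how much of the efficacy estimate comes from stops.

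A reader might go further and infer that an abrupt stop and a taper score alike on Hypothesis 2. They do not under section D's denominator (18.9% against 17.5% above); they would only if all patients were counted. A reader might also infer that the efficacy outcome and the harm are the same event. They are not: Eq. 2 is visit-level and classes no patient as a responder, and the share can also fall through fewer high-dose starts or lower doses.

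**Conclusion.** The point holds as a gap in analysis and reporting. An abrupt stop always lowers weekly MME, and by more than a reduction does. It lowers the high-dose share unless all of a clinician's opioid patients are high dose, when the share does not move; if a clinician stops all opioids, the post-period share is undefined. An excess of stops in the letter arm could be counted as benefit and go unreported.

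The sizes rest on assumed panels and event rates. The documents do not support the stronger conclusion that a positive result would consist of adverse events or could never indicate judicious prescribing: they give no stop rate, and only a between-arm excess matters. The synopsis and section D treat the high-dose outcome as secondary although section B.a lists it under primary hypotheses. The weekly-MME part of the point does not depend on which applies.

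**What to change.** Keep the primary and high-dose endpoints as planned. Add two prespecified supportive analyses to section D, reported whether or not any difference is significant:

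1. By arm, with confidence intervals that allow for clustering, the disposition of patients at 50 daily MME or more in the pre-period: still high-dose; reduced below 50; abruptly discontinued; died, or no further prescription with reason unknown. The last category is needed because no all-cause death linkage is described for Los Angeles.
2. How much of the between-arm difference in weekly MME comes from abruptly discontinued patients.

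Both should use one written operational definition of abrupt discontinuation, the same as for the section C.a comparison, which needs it anyway. The trial team should set it before outcome data are seen.

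A composite that scores abrupt stops as failures can be an optional sensitivity analysis. It should not replace the endpoint: it would follow a closed cohort of pre-period patients and miss new high-dose starts, which is a different estimand.

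The outpatient prescribing records and study identifiers are already planned for the limited data set. The cost is some patient-level analysis, and possibly a less favourable reading of a positive result.
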